**Table 8 Safety Laboratory Assessments**

Hematology			
Platelet count	Automated WBC differential:		
RBC count	Neutrophils		
WBC count (absolute)	Lymphocytes		
Hemoglobin	Monocytes		
Hematocrit	Eosinophils		
MCV	Basophils		
Clinical Chemistry			
BUN	Potassium	AST	Total bilirubin a
Creatinine	Chloride	ALT	Albumin
Glucose c	Total CO 2	Alkaline phosphatase	Creatine phosphokinase
Sodium	Lipase	Phosphate	Creatinine clearance b
Fasting Lipid Paneld			
Total cholesterol			
HDL cholesterol			
LDL cholesterol			
Triglycerides			
Other Tests			
Plasma HIV-1 RNA e			
CD4+ and CD8+ cell counts [CD4/CD8 ratio] f			
Peripheral Blood Mononuclear Cells (PBMCs): Day 1, Week 48, Week 96, Week 152 Withdrawal only			
Hepatitis B (HBsAg), anti-HBc, anti-HBsAg, and hepatitis C antibody (Screening) g			
Syphilis serology + Reflex Rapid Plasma Reagin (RPR) (Screening and Baseline)			
Prothrombin Time (PT)/International Normalized Ratio (INR)/ Partial Thromboplastin Time (PTT)			
Pregnancy test for women of childbearing potential h			
Urinalysis, urine albumin/creatinine ratio, and urine protein/creatinine ratio, urine phosphate			
Genetics Sample			
Follicle stimulating hormone (FSH) and estradiol (only for instances when postmenopausal status is questionable)			

MCV = mean corpuscular volume, RBC = red blood cells, WBC = white blood cells, BUN = Blood urea nitrogen, AST=aspartate aminotransferase, ALT = alanine aminotransferase, CO2 = carbon dioxide, HDL = high density lipoprotein, LDL = low density lipoprotein, HBsAg= hepatitis B virus surface antigen, PT/INR = prothrombin time/international normalized ratio.

- Direct bilirubin will be reflexively performed for all total bilirubin values  $>1.5 \times \text{ULN}$ .
- Glomerular filtration rate (GFR) will be estimated by the central laboratory using the Chronic Kidney Disease Epidemiology Collaboration (CKD-EPI) [Levey, 2009].
- For fasting glucose assessments, an overnight fast is preferred; however, a minimum of a 6-hour fast is acceptable for participants with afternoon appointments.
- For fasting lipids assessments, an overnight fast is preferred; however, a minimum of a 6-hour fast is acceptable for participants with afternoon appointments.
- For participants meeting virologic withdrawal criteria, plasma samples will be analyzed in attempt to obtain genotype/phenotype data.
- CD8+ cells will only be reported at Baseline, Day 1, Weeks 4b, 24, 48, 96 and 152.
- HBV DNA will only be performed for participants with a positive anti-HBc and negative HBsAg and negative anti-HBs (past and/or current evidence).
- Urine pregnancy test/ serum pregnancy test will be performed according to the Time and Events Table (Section 7.1).

### 7.4.3. Adverse Events (AE) and Serious Adverse Events (SAEs)

The investigator and their designees are responsible for detecting, documenting and reporting events that meet the definition of an AE or SAE.

Please refer to [Appendix 10](#) in Section [11.10](#) for study management information during the COVID-19 pandemic.

Reporting for medical device deficiencies are covered in Section [11.2](#)

#### 7.4.3.1. Time period and Frequency for collecting AE and SAE information

- Any SAEs assessed as related to study participation (e.g., protocol-mandated procedures, invasive tests, or change in existing therapy) or related to a GSK product will be recorded from the time a participant consents to participate in the study up to and including any follow-up contact.
- All SAEs will be recorded and reported to the sponsor or designee immediately and under no circumstance should this exceed 24 hours. The investigator will submit any updated SAE data to the sponsor within 24 hours of it being available.
- AEs will be collected from the start of Study Treatment until the final follow-up contact, at the timepoints specified in the Time and Events Table (Section [7.1](#)).
- All AEs and SAEs associated with medical device deficiencies for associated person (iespouse, caregiver, site staff...) will be collected. The associated person will be provided with a safety reporting information and authorization letter.
- Medical occurrences that begin prior to the start of study treatment but after obtaining informed consent may be recorded on the Medical History/Current Medical Conditions section of the eCRF.
- The method of recording, evaluating and assessing causality of AEs and SAEs plus procedures for completing and transmitting SAE reports to GSK are provided in Section [11.6](#), [Appendix 6](#)
- Investigators are not obligated to actively seek AEs or SAEs in former study participants. However, if the investigator learns of any SAE, including a death, at any time after a participant has been discharged from the study, and he/she considers the event reasonably related to the study treatment or study participation, the investigator must promptly notify GSK.

#### 7.4.3.2. Method of Detecting AEs and SAEs

Care will be taken not to introduce bias when detecting AEs and/or SAEs. Open-ended and non-leading verbal questioning of the participant is the preferred method to inquire about AE occurrence. Appropriate questions include:

- “How are you feeling?”
- “Have you had any (other) medical problems since your last visit/contact?”

- “Have you taken any new medicines, other than those provided in this study, since your last visit/contact?”

#### **7.4.3.3. Follow-up of AEs and SAEs**

After the initial AE/SAE report, the investigator is required to proactively follow each participant at subsequent visits/contacts. All SAEs, and non-serious AEs of special interest (as defined in Section 7.4.5) will be followed until resolution, until the condition stabilizes, until the event is otherwise explained, or until the participant is lost to follow-up (as defined in Section 5.5). Further information on follow-up procedures is given in Section 11.6, Appendix 6).

#### **7.4.3.4. Prompt Reporting of Serious Adverse Events and Other Events**

SAEs, pregnancies, and liver function abnormalities meeting pre-defined criteria will be reported promptly by the investigator to the medical monitor as described in Table 9 once the investigator determines that the event meets the protocol definition for that event. Any seizure or suspected seizure should be reported in an expedited manner, as noted in Table 9.

Criteria for liver chemistry stopping and follow-up criteria are in Section 5.5.1.

**Table 9 Reporting of Serious Adverse Events and Other Events**

Type of Event a	Initial Reports		Follow-up Information on a Previous Report	
	Time Frame	Documents	Time Frame	Documents
All SAEs	24 hours	"SAE" data collection tool	24 hours	Updated "SAE" data collection tool
Cardiovascular or death event	Initial and follow-up reports to be completed when the cardiovascular event or death is reported a	"CV events" and/or "death" data collection tool(s) if applicable	Initial and follow-up reports to be completed when the cardiovascular event or death is reported a	Updated "CV events" and/or "death" data collection tool(s) if applicable
Pregnancy	24 hours	"Pregnancy Notification Form"	Within 24 hours of investigator awareness of pregnancy outcome	"Pregnancy Follow-up Form" and SAE if required
Seizure or suspected seizure	24 hours	eCRF	24 hours	eCRF
Suspected ABC HSR in participants receiving Oral SOC during the Long-Term Follow-Up Phase b	1 week	ABC HSR eCRF	1 week	Updated ABC HSR eCRF
ALT $\geq$ 3 $\times$ ULN and bilirubin $\geq$ 2 $\times$ ULN (>35% direct) (or ALT $\geq$ 3 $\times$ ULN)	24 hours c	"SAE" data collection tool. "Liver Event eCRF" and "Liver Imaging" and/or "Liver Biopsy" eCRFs, if applicable d	24 hours	Updated "SAE" data collection tool/"Liver Event" documents d

Type of Event e	Initial Reports		Follow-up Information on a Previous Report	
	Time Frame	Documents	Time Frame	Documents
ALT ≥ 5 × ULN that persists ≥ 2 weeks	24 hours c	Liver Event eCRF d	24 hours	Updated Liver Event eCRF d
ALT ≥ 8 × ULN	24 hours c	Liver Event eCRF d	24 hours	Updated Liver Event eCRF d
ALT ≥ 3 × ULN (if baseline ALT is < ULN) or ALT ≥ 3 fold increase from baseline value with appearance or worsening of symptoms of hepatitis or hypersensitivity	24 hours c	Liver Event eCRF d	24 hours	Updated Liver Event eCRF d

- Additional details and time frames for reporting supplementary information for cardiovascular and death events are provided in Section 7.4.3.7 and Section 7.4.3.8, respectively.
- ABC HSR eCRF only required if event meets one of the ICH E2A definitions of seriousness.
- GSK must be contacted at onset of liver chemistry elevations to discuss participant safety.
- Liver event documents (i.e., "Liver Event eCRF" and updates, "Liver Imaging eCRF" and/or "Liver Biopsy eCRF", as applicable) should be completed as soon as possible.
- Please refer to Section 11.12 (Appendix 12) for additional details around Medical Device Deficiencies reporting requirements.

### SAE reporting to GSK via electronic data collection tool

- Primary mechanism for reporting SAEs to GSK will be the electronic data collection tool.
- If the electronic system is unavailable for greater than 24 hours, the site will use the paper SAE data collection tool and fax it to the Medical Monitor.
- Site will enter the serious adverse event data into the electronic system as soon as it becomes available.
- After the study is completed at a given site, the electronic data collection tool (e.g., InForm system) will be taken off-line to prevent the entry of new data or changes to existing data.
- If a site receives a report of a new SAE from a study participant or receives updated data on a previously reported SAE after the electronic data collection tool has been taken off-line, the site can report this information on a paper SAE form or to the Medical Monitor by telephone.
- Contacts for SAE receipt can be found in the Study Reference Manual.
- The investigator will be required to confirm review of the SAE causality by ticking the 'reviewed' box at the bottom of the eCRF page within 72 hours of submission of the SAE.

The method of recording, evaluating, and follow-up of AEs and SAEs plus procedures for completing and transmitting SAE reports to the medical monitor are provided in the SPM. Procedures for post study AEs/SAEs are provided in the SPM. Primary and

secondary Medical Monitor/SAE contact information is provided in the Study Reference Manual .

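### The paper back-up for SAE reports is triggered by the length of the outage, not by the SAE clock, so in some outages following it forces a report past the 24-hour limit

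*Protocol*

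**What the plan says.** The limit is in Protocol Section 7.4.3.1: "All SAEs will be recorded and reported to the sponsor or designee immediately and under no circumstance should this exceed 24 hours". The same section covers follow-up data: "The investigator will submit any updated SAE data to the sponsor within 24 hours of it being available". Table 9 repeats the figure ("All SAEs 24 hours") and gives 24 hours for follow-up SAE information as well. Section 7.4.3.4 says when prompt reporting is due: "once the investigator determines that the event meets the protocol definition for that event".

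The route is set out under the heading on SAE reporting via the electronic data collection tool. "Primary mechanism for reporting SAEs to GSK will be the electronic data collection tool". For an outage during the study it says: "If the electronic system is unavailable for greater than 24 hours, the site will use the paper SAE data collection tool". The paper form is then faxed to the Medical Monitor, and the data are entered electronically later.

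One other non-electronic route appears there. It covers an SAE that comes to light after the tool has been taken off-line because the study has finished at that site: "the site can report this information on a paper SAE form or to the Medical Monitor by telephone". That route has no waiting period, but it does not apply to an outage while the study is running.

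**The concern.** The limit is counted from when the investigator determines that the event is an SAE. The back-up is counted from when the system fails. The two clocks are independent, and the waiting time on the second is as long as the whole allowance on the first. A site caught by an outage may therefore have two instructions that it cannot both obey: wait for the paper trigger, or meet the deadline.

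At stake is the timeliness of safety reporting. Section 7.4.3.6 states that prompt SAE notification is essential to the sponsor's legal and ethical obligations. A back-up procedure exists to protect the deadline when the main route fails, and this one need not do so.

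**Working it through.** The plan gives no figure to reproduce. The check is a timeline.

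**Inputs**
- Reporting limit: 24 hours, for initial reports and for updates (Section 7.4.3.1, Table 9).
- Clock start: the investigator's determination (Section 7.4.3.4). For an update, the time the new data become available (Section 7.4.3.1).
- Paper trigger: system unavailable for more than 24 hours (Section 7.4.3.4).
- Outage timing and duration: not in the protocol, so varied below as assumptions.

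**Set-up.** Put determination at hour 0. The outage starts at hour u (negative if it was already running) and lasts D hours. The SAE has not been entered when the system fails. Under the literal instruction:
- if D is 24 or less, paper does not open and the earliest report is electronic, at hour u + D;
- if D exceeds 24, the earliest report is on paper, just after hour u + 24.

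**Cases**

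| Outage start u | Duration D | Earliest report | Within 24 h? |
|---|---|---|---|
| 0 | 20 | 0 + 20 = 20 h, electronic | Yes |
| 0 | over 24 | just after 0 + 24 = 24 h, paper | No |
| 6 | 20 | 6 + 20 = 26 h, electronic | No |
| 6 | over 24 | just after 6 + 24 = 30 h, paper | No |
| −10 | over 24 | just after −10 + 24 = 14 h, paper | Yes |

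**General condition.** If u is 0 or more, the limit is missed whenever u + D exceeds 24, that is, whenever the outage starts at or after determination and is still running at the deadline. If u is negative and the outage is counted from its true start, a report is always possible before hour 24: electronically at u + D when D is 24 or less, or on paper just after u + 24 otherwise.

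**How the site counts.** The last row assumes that the site knows when the system really failed. If it counts from its own first failed attempt to enter the SAE, at hour f, then f cannot be before hour 0 and paper opens only after hour f + 24, which is past the limit. With u = −10, this matters when the outage is still running at hour 24, so when D exceeds 24 + 10 = 34 hours. Paper then opens after hour 24 instead of just after hour 14.

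The arithmetic is the same for an update, with hour 0 at the time the new data are available.

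**The case against.** The strongest reply is that the protocol calls the electronic tool primary, not exclusive. The back-up sentence says when paper will be used and does not forbid earlier paper, fax or telephone contact. Section 7.4.3.1 allows no exception, so a site near its deadline should report by any means it has. That is a workable reading, and a careful site might adopt it. But it asks the site to look past the one instruction written for this situation. The stated trigger and the stated limit still do not fit together.

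The trigger could also be read as covering an outage known in advance to exceed 24 hours, so that paper could start at once. The sentence does not say so, and the case with u = 6 and D = 20 would remain.

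Section 11.6.6 (Appendix 6) and the Study Procedures Manual also deal with sending SAE reports. They were not available for this check and may give a faster back-up. If so, the practical risk falls, but Section 7.4.3.4 would still need to agree with them.

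A reader might infer more than the text supports:
- **That every outage breaks the limit.** It does not, as the first and last rows of the table show.
- **That delays reach 36 or 47 hours.** Those totals (12 + 24 and 23 + 24) need a site that had already held a known SAE for 12 or 23 hours, although Section 7.4.3.1 says to report immediately. That part of the delay is the site's own.
- **That the IDMC or next-dose decisions would suffer.** Section 4.2.6 has the IDMC review data at predetermined times. Sections 7.4.4.1, 7.4.4.3 and 7.4.4.4 handle toxicity through the investigator and the Medical Monitor, not through eCRF entry.
- **That liver events are equally exposed.** Section 5.5.1.1 separately requires events meeting the liver stopping criteria to be reported to the Medical Monitor within 24 hours, and a note to Table 9 requires contact with the sponsor at onset.

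**Conclusion.** The point holds in limited form. The outage instruction in Section 7.4.3.4 conflicts with the limit in Section 7.4.3.1 and Table 9 when the outage starts at or after determination and lasts past the deadline. It also conflicts when the site counts from its first failed entry and the outage outlasts the deadline. For a site that acts promptly, the report is then just over 24 hours at best. Because the limit admits no exception, one ordinary scenario of this kind is enough to make the two passages inconsistent.

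This rests on reading the trigger literally and on the SAE not having been entered before the system failed. The frequency of outages is unknown, so the number of reports affected cannot be estimated. It is an operational inconsistency in safety reporting, with no bearing on sample size, power, alpha or any endpoint.

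**What to change.** Reconcile Section 7.4.3.1, Table 9 and Section 7.4.3.4 by replacing the outage trigger with wording such as: *If the electronic system is unavailable and an SAE or update cannot be entered in time to meet the 24-hour limit, the site will send the paper SAE form by fax to the Medical Monitor within those 24 hours, and enter the data electronically once the system is available.*

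Keep any back-up described in Section 11.6.6 and the Study Procedures Manual consistent with this. Apply the same back-up to seizure and suspected seizure reports, for which Table 9 sets 24 hours and lists the eCRF as the only document.

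The cost is one sentence in the protocol, a matching line in the manual, and occasional duplicate entry of a report first sent on paper. No analysis or clinical rule changes.

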#### **7.4.3.5. Disease-Related Events and/or Disease-Related Outcomes Not Qualifying as SAEs**

Disease related events (DREs) or outcomes listed in the CDC Classification System for HIV-1 Infections ([Appendix 4](#)) can be serious/life threatening and will be recorded on the HIV-Associated Conditions eCRF page if they occur. However, these individual events or outcomes, as well as any sign, symptom, diagnosis, illness, and/or clinical laboratory abnormality that can be linked to any of these events or outcomes are not reported to GSK as AEs and SAEs even though such event or outcome may meet the definition of an AE or SAE. However, if any of the following conditions applies, then the event must be recorded and reported as an AE or SAE (According to severity ):

- The investigator determines that the event or outcome qualifies as an SAE under part ‘other situations’ of the SAE definition (see [Section 11.6.2](#)), or
- The event is, in the investigator’s opinion, of greater intensity, frequency, or duration than expected for the individual participant, or
- The investigator considers that there is a reasonable possibility that the event was related to treatment with the investigational product, or
- Death occurring for any reason during a study, including death due to a disease-related event, will always be reported promptly.
- Lymphomas and invasive cervical carcinomas are excluded from this exemption; they must be reported as SAEs even if they are considered to be HIV-related.

**If any of the above conditions is met, then record the event on either the AE or SAE page (according to severity) in addition to the HIV Associated Conditions eCRF page. If it is categorized as an SAE, report promptly (i.e., expedited reporting, see [Section 7.4.3.4](#)) to GSK.**

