### **6.11. Treatment of Study Treatment Overdose**

For participants receiving Oral CAB, any tablet intake exceeding a total daily dose of 30 mg will be considered an overdose. For participants receiving oral RPV, any dose exceeding a total daily dose of 25 mg will be considered an overdose.

For CAB LA and RPV LA, any single dose in excess of the studied doses will be considered an overdose.

Should IM maladministration, specifically overdose or inadvertent IV dosing, be suspected at any time, the participant will stay onsite for approximately 2-3 hours post dose for safety monitoring and an ECG will be performed at 2 hours post dose. The Medical Monitor will be notified in the event of a suspected maladministration.

In the event of suspected maladministration, additional PK samples will be drawn at 2 hours post dosing for evaluation of CAB and RPV concentrations.

For the purposes of this study, an overdose is not an AE (refer to Section 11.6.1 ) unless it is accompanied by a clinical manifestation associated with the overdose. If the clinical manifestation presents with serious criteria, the event is a SAE (see Section 11.6.2).

If an overdose occurs and is associated with an adverse event requiring action, all study medications must be temporarily discontinued until the adverse event resolves.

The Investigator should use clinical judgement in treating overdose, as ViiV Healthcare is unable to recommend specific treatment.

In the event of an overdose the investigator or treating physician should:

1. Contact the Medical Monitor immediately

2. Closely monitor the participant for adverse events (AEs)/serious adverse events (SAEs) and laboratory abnormalities until the IP can no longer be detected systemically (at least 5 days for oral CAB and oral RPV, and 52 weeks for CAB LA and RPV LA)
3. Obtain a plasma sample for pharmacokinetic (PK) analysis if possible within 2 days from the date of the last dose of study treatment if requested by the Medical Monitor (determined on a case-by-case basis).
4. Document the quantity of the excess dose as well as the duration of the overdosing in the CRF.

Decisions regarding dose interruptions or modifications will be made by the investigator in consultation with the Medical Monitor based on the clinical evaluation of the participant.

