#### 7.4.4. Toxicity Management

Adverse events that occur during the trial should be evaluated by the Investigator and graded according to the Division of AIDS (DAIDS) toxicity scales (See Section 11.2. “Division of AIDS Table for Grading the Severity of Adult and Pediatric Adverse Events”). Additional information regarding detecting, documenting and reporting AEs and SAEs are available in Section 7.4.3 and Section 11.6.

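### Section 7.4.3.5 chooses between AE and SAE for reportable HIV-related events by severity, although SAE status elsewhere in the protocol rests on seriousness

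*Protocol*

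**What the plan says.** Section 7.4.3.5 sends conditions on the CDC list for HIV infection to the HIV-Associated Conditions eCRF page and keeps them out of AE and SAE reporting, even where they would meet either definition. Five conditions lift that exemption.

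The routing rule for an event that meets one of them appears twice. The sentence introducing the list says "then the event must be recorded and reported as an AE or SAE (According to severity"). The closing instruction repeats it: "then record the event on either the AE or SAE page (according to severity"). The next sentence makes expedited reporting depend on the result: "If it is categorized as an SAE, report promptly".

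Three other places show how the protocol uses the two concepts:

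- Section 7.4.4 has adverse events "graded according to the Division of AIDS (DAIDS) toxicity scales", using a table whose title calls it a severity grading table.
- Section 6.11, on overdose, decides SAE status differently and refers to Section 11.6.2: "If the clinical manifestation presents with serious criteria, the event is a SAE".
- A footnote to Table 9 says "ABC HSR eCRF only required if event meets one of the ICH E2A definitions of seriousness".

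The general reporting clock is in Section 7.4.3.1: "All SAEs will be recorded and reported to the sponsor or designee immediately and under no circumstance should this exceed 24 hours".

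**The concern.** Severity and seriousness are separate attributes of an adverse event. Severity describes intensity and is graded. Seriousness is a yes-or-no classification by defined criteria, and it triggers expedited reporting. Section 7.4.3.5 names the first where the second is needed.

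The events at stake are the ones the section is meant to bring back into safety reporting, including those the investigator thinks may be related to the investigational product. Section 7.4.3.6 treats prompt notification of treatment-related SAEs as essential to the sponsor's legal and ethical duties. If a site follows the words on the page, a serious event of this kind could be recorded as an ordinary AE and not be expedited. The opposite error, a severe but non-serious event entered as an SAE, is equally open.

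**Working it through.** No arithmetic applies: the protocol states no figure on this point, and the question is which criterion selects the page. The check is a comparison of texts.

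**1. Is this operative text?** Yes. Both statements stand in the body of Section 7.4.3.5, not in the amendment summary.

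**2. What does severity mean here?** Section 7.4.4 ties it to the DAIDS scales. Section 7.4.4.1 announces management guidance by the severity of the AE, and Sections 7.4.4.2 to 7.4.4.4 supply it under Grade 1 or 2, Grade 3 and Grade 4. So severity is the grade.

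**3. What makes an event an SAE?** Section 6.11 uses serious criteria and refers to Section 11.6.2. The Table 9 footnote uses the ICH E2A notion of seriousness. Neither uses a grade.

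**4. Can the severity rule be applied as written?** No. Section 7.4.3.5 gives no grade at which an event moves from the AE page to the SAE page. A site must invent a cut-off or disregard the words.

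**5. Is the rule consistent with its own list?** No. The closing instruction covers all five conditions:

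| Condition | Is the outcome already fixed by its own wording? |
|---|---|
| Qualifies under the other-situations part of the SAE definition | Yes, it is an SAE by that definition |
| Intensity, frequency or duration beyond what is expected for the participant | No |
| Reasonable possibility of relation to the investigational product | No |
| Death | Yes, always reported promptly |
| Lymphoma or invasive cervical carcinoma | Yes, must be reported as an SAE |

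For the first and last rows, offering the AE page as an alternative contradicts the row itself. Three of the five are protected, so 5 − 3 = 2 depend on the page choice.

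**6. Does the general 24-hour rule close the gap for those two?** Only in part. Section 7.4.3.1 covers all SAEs, but Section 7.4.3.5 is the specific exception for disease-related events. Within it, the page choice determines the route back into expedited reporting. A site that has recorded the event as an AE on grounds of severity has, by that section, no instruction to expedite it.

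**The case against.** The strongest reply is that this is one wrong word whose intended meaning is obvious. Because no grade cut-off is stated, a trained investigator would fall back on the SAE definition, which Section 7.4.3.5 itself mentions through Section 11.6.2. Section 7.4.3 makes investigators responsible for events meeting the AE or SAE definition, and Section 7.4.3.1 and Table 9 set 24 hours for every SAE. Sections 11.6.2, 11.6.5 and 11.6.6 are in the part of the protocol not available here and may separate the two concepts clearly. The comparison texts on overdose and on the abacavir hypersensitivity form are also indirect.

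Much of this stands as a limit on harm. Many sites would apply seriousness anyway, and a safeguard in the unseen sections cannot be excluded. The indirect texts still show that the protocol treats seriousness as distinct from grade. None of this makes severity the right criterion, and relying on investigators to ignore an instruction is a weak control for expedited reporting.

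A reader might also infer that the rule sends every low-grade serious event to the AE page and every high-grade non-serious event to the SAE page. The text does not say that. With no cut-off, the documents support only that such misplacement could occur.

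**Conclusion.** Section 7.4.3.5 is wrong as written, and the defect is minor. It uses severity where SAE status should follow seriousness, and it conflicts with its own conditions that already fix SAE status. The exposed events are serious ones that are worse than expected or possibly related to the investigational product, which could miss the expedited route, and severe but non-serious ones, which could be entered as SAEs.

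The size cannot be quantified. The document gives no rate of HIV-associated conditions, no count of disease-related SAEs and no fraction expected to meet a condition.

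A reader might go further and conclude that SAE counts are distorted between the arms. The document does not support this. The same rule applies to Q4W and Q8W, nothing shown makes it act differently by arm, and the safety endpoints in Section 3 concern AE incidence and severity, discontinuation due to AEs and laboratory data, not SAE counts by arm. Nor does every misplaced event necessarily lose its 24-hour report, since the general rule may still catch it.

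The conclusion assumes that severity has the same meaning here as in Section 7.4.4 and that Section 11.6.2 defines SAEs by seriousness, as Section 6.11 indicates. The primary analysis and the sample size are unaffected.

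**What to change.** In both places in Section 7.4.3.5, replace the bracketed reference to severity with *according to the seriousness criteria in Section 11.6.2*. State that the DAIDS grade is recorded separately and does not decide which page is used. This brings the section into line with Sections 6.11 and 7.4.3.1 and with Table 9.

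The cost is a few words in one section, with a matching check of the eCRF completion guidance. No treatment, visit, endpoint or analysis changes.
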